5 OUTCOMES

5.1 Primary Outcomes

5.1.1 *Domain: Aerobic Capacity*

Timeframe: -2, 0 to 12 weeks

Measurement: Maximal volume of inspired oxygen per minute per kilogram of body weight of the participant (VO₂Max).

- Measured during a maximal exercise bout. Maximal defined as two out of three of the following:
 - Plateau in volume of inspired oxygen per minute. So that increase in workload results in no increase in inspired oxygen.
 - Ratio between volume of inspired oxygen and expired carbondioxide more than 1.1
 - Exertion by BORG scale 18, 19 or 20.

If the bout is considered a maximal bout, the VO₂max will be defined as the highest 30 second average oxygen uptake per minute per kilogram of bodyweight. (in ml/min/kg)

- Volumes of gases measured by indirect calorimetry.
- Heart rate during the bout is measured by PolarFlow™ and added to the CosMed system.
- In order to test whether changes in this measurement is just due to changes in weight, absolute VO₂max (not corrected for patient weight) will also be reported.

5.1.2 *Domain: Fatigue – Patient reported*

Timeframe: 0 to 12 weeks.

Measurement:

- Patient reported outcome measure (PROM).
- Krupp's Fatigue severity scale³⁷, as the average of all 9 domains (0-7).
- This scale has been verified for use in Danish SLE patients³⁸.

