#### 3.9.2 Maximal aerobic capacity

Patients will perform a graded exercise test on a bicycle ergometer (Monark LC4, Monark Exercise AB, Vansbro, Sweden) at CFAS, to determine the maximal oxygen consumption (VO2 max).

Maximal workload (watt-max) will be estimated based on baseline physical activity, resting heart rate, weight, gender, age and waist circumference as per the method described by Nes et al.

Using this estimation participants will warm up for 5 minutes at 15% of their watt-max (rounded to nearest 10) and increase in steady increments of 1 minute each to reach their estimated 100% watt-max at 15 minutes (so an increase of 8,5% watt-max per minute). Following these 15 minutes, watt will be added in the same increments until exhaustion.

The patients will be encouraged to perform at their maximal effort by CFAS staff. The ventilation rate and expired CO2 and O2 will be measured by indirect calorimetric measurements (Quark b2, Cosmed, Rome, Italy.) The peak HR measured will serve as reference for relative intensity during the study.

This test will be done immediately following consent, and again at the first baseline day and at follow-up, to alleviate for habituation in the exercise group.

If for some reason the participant cannot do more than 7 minutes on this maximal aerobic capacity or they cannot increase their maximal heart rate above 120 minutes at the first test; another test will be done which is reduced to this new watt-max (reached at 15 minutes). This test will be done with a stress ECG monitoring to evaluate whether the participant suffers from a cardiac condition that limits their potential.

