5.3.14 Domain: Autonomic Nerve Function testing

Timeframe: 0-2 to 12-14 weeks

Description: By Vagus™, a device measuring heart rate and heart rate variability will measure:

Measurements:

- Resting heart rate
- Ratio between minimal and maximal heart rate when the subject is:
 - Rising from supine.
 - Controlled breathing exercises.
 - Doing the Valsalva maneuver.

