6 STUDY POPULATION, ANALYSIS SET AND STATISTICAL PRINCIPLES

Eligibility criteria have been previously published³⁵. In brief, the participants suffered from systemic lupus erythematosus, and fulfilled 10 or more points on the 2017 ACR/EULAR SLICC⁴³, were not pregnant, did not suffer from diabetes mellitus and were 18 years or older, both males and females were included.

As stated earlier, sample size calculation required 40 completers, the study included 55 participants.

Randomization was done in a 1:1 ratio, stratified on sex.

The statistical analyses will be carried out primarily in the modified intention to treat (mITT) population, excluding the participants who were randomized but were found ineligible as per the ineligibility criteria within the first week of randomization, while retaining the data from all other study participants as randomized regardless of compliance and study completion. Supplementary per protocol (PP) analyses will exclude data from participants in the exercise group who failed to show up for 80% or more of the exercise sessions (29 or more sessions needed attendance to be considered in the PP group).

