6.1 Statistical Methods

Evaluation of the treatment effect in the primary analyses will be performed using a constrained linear mixed effect model including sex, follow-up time (categorical), treatment, and the constrained treatment*time interaction as fixed effects, and with an unstructured covariance pattern to account for repeated measurements on each study participant; as a sensitivity analysis, the interaction between sex*time will also be considered, but not included in the main model, as there seem to be no interaction for this in exercisers without SLE at 12 weeks⁴⁴. Effect modification by IFNGS will be evaluated by further including IFNGS (continuous scale), the IFNGS- -time interaction, and the constrained treatment*time*IFNGS interaction in the linear mixed model. Missing data will be handled implicitly by maximum likelihood estimation in the linear mixed model.

For the exploratory outcomes in the oral glucose tolerance test and acute exercise bout domains blood was sampled 6 or 9 times (respectively) throughout the measurements, a linear mixed effect model will be used on summary scores (such as DI or Matsuda Index).

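### The gas criterion for a maximal VO₂max test in SAP 5.1.1, read in the order written, points away from maximal effort and should be restated before tests are classified

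*SAP*

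**What the plan says.** SAP 5.1.1 measures aerobic capacity at -2, 0 and 12 weeks. A bout is maximal when at least two of three things hold: oxygen uptake reaches a plateau, the Borg rating is 18, 19 or 20, and the gas criterion is met, worded as "Ratio between volume of inspired oxygen and expired carbondioxide more than 1.1". The endpoint depends on that classification: "If the bout is considered a maximal bout, the VO₂max will be defined as the highest 30 second average oxygen uptake". The section does not say what is done with a completed test that is not maximal.

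SAP 6.1 states: "Missing data will be handled implicitly by maximum likelihood estimation in the linear mixed model". The one sensitivity analysis it names for the primary model concerns sex: "as a sensitivity analysis, the interaction between sex*time will also be considered".

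Protocol 3.9.2 describes the same graded test. On load it says: "Following these 15 minutes, watt will be added in the same increments until exhaustion". On timing it says: "This test will be done immediately following consent, and again at the first baseline day and at follow-up". It measures both gases but gives no gas criterion and no definition of a maximal test. Its only retest rule applies to the first test and uses test duration or heart rate, not the two-of-three rule.

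**The concern.** The gas line names oxygen first and carbon dioxide second, then asks for a ratio above 1.1. Computed in that order, it rewards tests in which CO₂ output is well below O₂ uptake. That CO₂ output rises relative to O₂ uptake with effort is general physiology, not something the documents state. The line does sit under the definition of a maximal bout, though, so a threshold in the low direction cannot be what was meant.

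This is an operative threshold and not background text. It decides which tests give a value for the first primary endpoint. Under SAP 3.1 and 6.2 the question of effect modification by interferon signature (1b) is tested only if the treatment effect on VO₂max (1a) is significant. If someone coded the line literally, some tests would be kept and others set aside wrongly on the way to both hypotheses.

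A smaller matter follows from the same rule. Whether a test is maximal depends partly on effort, and the other primary endpoint is fatigue. If non-maximal tests drop out, the loss may be related to effort, and no planned analysis or count would show it.

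**Working it through.** **Inputs.** From SAP 5.1.1: the threshold 1.1, the order oxygen then carbon dioxide, and the two-of-three rule. From SAP 4: 55 participants. From SAP 5.1.1 and Protocol 3.9.2: three routine tests each. The 1.1 is a definition, so there is no plan figure to reproduce.

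**Step 1, invert the ratio.** O₂/CO₂ > 1.1 is the same as CO₂/O₂ < 1/1.1 = 0.909.

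**Step 2, two illustrative tests** (gas volumes in L/min, chosen for illustration).
- O₂ 2.0, CO₂ 2.3: CO₂/O₂ = 1.15 and O₂/CO₂ = 0.87. It fails in the written order and passes in the reversed order.
- O₂ 2.0, CO₂ 1.7: CO₂/O₂ = 0.85 and O₂/CO₂ = 1.18. It passes in the written order and fails in the reversed order.

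**Step 3, carry this through the two-of-three rule.**
- Plateau and Borg both met: maximal whatever the gas result. The order does not matter.
- Neither met: not maximal whatever the gas result. The order does not matter.
- Exactly one met: the gas criterion decides. With CO₂/O₂ below 0.909 the written order accepts the test and the reversed order rejects it. With CO₂/O₂ above 1.1 the written order rejects it and the reversed order accepts it. From 0.909 to 1.1 both orders reject it.

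So only tests with exactly one of plateau and Borg, and CO₂/O₂ outside 0.909 to 1.1, are classified differently.

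**Step 4, how many tests.** The routine schedule is 55 × 3 = 165 tests, 110 before the intervention and 55 after. This is not a ceiling, because the protocol's retest rule can add a test. The documents do not give the share falling in the affected group.

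**Step 5, completed tests that fail.** VO₂max is defined only for a maximal bout, so a failed test has no value and most naturally becomes missing in the mixed model. As a generic illustration only, a share f of 12-week values lost at random and equally by arm widens the interval for 1a by 1/√(1 − f) − 1: 2.6%, 5.4% and 11.8% for assumed f of 5%, 10% and 20%. This holds for values lost for any reason. It does not measure effort-related loss, and no failure rate is given.

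**The case against.** The best defence is that a ratio between two quantities does not strictly fix numerator and denominator. SAP 5.3.14 is similarly loose: "Ratio between minimal and maximal heart rate when the subject is". SAP 5.1.1 is informal elsewhere too, using inspired volume and oxygen uptake for the same measure. Nothing suggests that anyone would apply the reversed order, and SAP 4 refers to a published protocol preprint that may settle it. This stands as far as it goes: the line is probably a slip. But a line that decides which tests give the primary endpoint should not depend on the reader to correct it, and neither supplied document does.

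On failed tests the defence is stronger. The definition and the maximum-likelihood sentence together already give a default. A reader might infer that the SAP contradicts itself, because its analysis set is described as "while retaining the data from all other study participants as randomized regardless of compliance and study completion". That sentence concerns which participants are analysed, not whether a single measurement is valid, so it does not create a conflict.

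Several safeguards also limit the harm. The test runs to exhaustion with encouragement, and only the Borg criterion is self-rated. Protocol 3.8 has blinded staff meet patients at follow-up. With two tests before the intervention, one failed early test need not remove a participant's baseline value. The CONSORT diagram and the n per arm in Table 2 will show totals, and the analysis code is to be public. None of these promises a count of attended tests set aside as non-maximal.

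**Conclusion.** The gas criterion is wrong as written if taken in its written order, and it should be corrected because it is part of the definition of the first primary endpoint. The effect is confined to tests that meet exactly one of plateau and Borg and have CO₂/O₂ below 0.909 or above 1.1. The number of such tests is unknown.

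A reader might infer that tests were in fact misclassified, or that the VO₂max result is biased or underpowered for this reason. The documents support neither. They do not show how the ratio was computed, give no rate at which tests fail the rule, and give no basis for the size or direction of any bias.

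The handling of failed tests is secondary. The plan has a workable default, and the extra analysis and count suggested below are cheap checks on loss that may depend on effort, not correction of an error. The conclusion rests on the written order being taken literally and on the general physiological point that CO₂/O₂ rises with effort.

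**What to change.** Restate the criterion in SAP 5.1.1 as the volume of expired CO₂ divided by the volume of O₂ uptake, greater than 1.1. Confirm before analysis that tests were classified that way. SAP 8 has the plan published before statistical analysis starts, so the change belongs there. The cost is one line and one check of the classification.

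Optional:
- State that a completed non-maximal test is treated as missing in the primary model.
- Report maximal out of completed tests by arm and visit, for example as a row in eTable 6 (SAP 12.3).
- Run the same mixed model once with the highest 30-second average from every completed test at -2, 0 and 12 weeks, as a sensitivity analysis.

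These cost one sentence, one table row and one model run on data already recorded. The downside is that the all-tests analysis includes some sub-maximal values that may understate capacity, so it should stay a sensitivity analysis.

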5.2 Secondary Outcomes

5.2.1 *Domain: Physician evaluated changes in measures of SLE*

Timeframe: 0 to 12 weeks

Measurement: Y2K updated SLE disease activity (SLEDAI-2K) with the SELENA modifications³¹.

5.2.2 *Domain: Patient reported outcome quality of life.*

Timeframe: 0 to 12 weeks, and again as an exploratory analysis, at 1, 2 and 3 months following the intervention.

Measurement:

- Short Form (SF)-36 Health Survey (0-100)³⁹ - Possible scores range from 0 to 100, with higher scores representing better health status.
- Summed into the 8 domains.
- Summed into the 2 aggregate scores.

5.2.3 *Domain: Type 1 Interferon gene signature*

Timeframe: 0 to 12 weeks

Measurement: Pax-gene tubes withdrawn from fasting participants at baseline.

- Analyzed by Nanostring for genes related to IFN-signaling.⁴⁰
- Normalized to housekeeping genes
- Calculating a standardized z-score compared to the expression from 9 healthy controls

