### **3.9.9 mRNA expression analyses**

During withdrawal of whole blood from patients, 10mL will be transferred to a PAXgene Blood RNA tube (PreAnalytiX, Switzerland), which will then be incubated overnight at room temperature before processing, to complete lysis of nucleated blood cells.

RNA will then be isolated without external stimuli using the PAXgene Blood RNA Kit (Qiagen), following manufacturer instructions. The samples will then be spun in a Sigma 4k10 centrifuge to pellet the nucleic acids, which will then be resuspended, transferred to a PAXgene Shredder spin column and incubated in optimized buffers and Proteinase K to digest proteins. The shredder spin column will then be centrifuged again to homogenize the cell lysate and remove cell debris.

The supernatant of the flow-through fraction will then be transferred to a fresh microcentrifuge tube and ethanol will be added.

Then the lysate will be transferred to a PAXgene RNA spin column and spun briefly. This will cause RNA to bind to the spin column membrane and with several following wash steps, contaminants will be removed. In between these wash steps the spin column membrane will be treated with DNAase I to remove trace amounts of DNA. Hereafter RNA will be eluted in a buffer (BR5) and heat denatured. Whereafter RNA will be stored at -80°C.

When ready for analysis, these tubes will be thawed on ice and total RNA will be quantified using RT-qPCR or Nanostring (Thermo Fisher, Waltham, MA, USA) technology.

We will then analyze these samples for mRNA gene expression analysis for IFNGS, TNF-related genes, IL-6-Related genes as well as housekeeping genes. In total we will analyze mRNA expression for around 100 different genes. The abbreviations and types of genes as well as their function have been looked up using Genecards.org.

The expression of each transcript will be normalized to an average expression of housekeeping genes. We plan to analyze the mRNA expression of three housekeeping genes.

Afterwards, like the process described by Kim et al. we will determine both a Z-score and a Geomean mRNA expression score for all subjects:

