### 3.9.9.1 Standardized mRNA expression scores

Samples will be compared to samples from 10 healthy in-house volunteers, to give a Z-Score:

$$Z - Score_{Gene} = \frac{[Gene Count - Mean (HC gene expression)]}{[Standard Deviation (HC Gene expression)]}$$

This Z-Score can then be averaged for each module to give a standardized mRNA expression score for all of the modalities below.

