### 3.9.9.2 Geomean mRNA expression Score

Alternatively, the geometric mean of mRNA expressed genes can be calculated as:

$$Geomean - IFNScore = \sqrt[n]{g_1 \cdot g_2 \cdot g_3 \dots \cdot g_n}$$

So for example:

$$GEOMEAN, M5.12$$

$$= \sqrt[8]{[ADAR] \cdot [BST2] \cdot [GBP2] \cdot [IRF9] \cdot [ISG20] \cdot [SP100] \cdot [TRIM21] \cdot [TRIM25]}$$

Which gives a score for M5.12 that can be compared across patients with SLE.

This geomean score can be done in absence of healthy volunteers and could be useful for further clinical practice.

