#### 3.9.9.3.1 Chiche and Chaussabel et al. method

The Chiche and Chaussabel et al. method will be done in WB of modules defined by them as related to IFNGS for SLE; M1.2, M3.4 and M5.12 (see Table 2).

These genes are the same as defined in the modular gene expression by Chaussabel et al. and have been used for SLE patients.

3.9.9.3.1.1 M1.2	20 Genes	
Abbreviation	Gene	Function  (according to Genecards.org)
CXCL10	chemokine (C-X-C motif) ligand 10	Protein Coding gene. Diseases associated with CXCL10 include Periapical Periodontitis and Viral Encephalitis. Among its related pathways are Innate Immune System and PEDF Induced Signaling. Gene Ontology (GO) annotations related to this gene include

		signaling receptor binding and chemokine activity. An important paralog of this gene is CXCL9.
DDX60	DEAD (Asp-Glu-Ala-Asp) box polypeptide 60	Protein Coding gene. Diseases associated with DDX60 include Lip Cancer and Autosomal Recessive Alport Syndrome. Gene Ontology (GO) annotations related to this gene include nucleic acid binding and hydrolase activity. An important paralog of this gene is DDX60L.
EPSTI1	epithelial stromal interaction 1	Protein Coding gene. Diseases associated with EPSTI1 include Lupus Erythematosus and Systemic Lupus Erythematosus.
HERC5	HECT and RLD domain containing E3 ubiquitin protein ligase 5	Protein Coding gene. Diseases associated with HERC5 include Influenza. Among its related pathways are RIG-I/MDA5 mediated induction of IFN-alpha/beta pathways and Innate Immune System. Gene Ontology (GO) annotations related to this gene include ubiquitin-protein transferase activity. An important paralog of this gene is HERC6.
IFI44	interferon-induced protein 44	Protein Coding gene. Diseases associated with IFI44 include Hepatitis D and Potocki-Shaffer Syndrome. An important paralog of this gene is IFI44L.
IFI44L	interferon-induced protein 44-like	Protein Coding gene. Diseases associated with IFI44L include Lymph Node Tuberculosis and Immunodeficiency 38 With Basal Ganglia Calcification. An important paralog of this gene is IFI44.

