### 3.9.9.3.2 El-Sherbiny et al. method

In addition to these we will evaluate mRNA for IFNGS as per El-Sherbiny et al. Who has segregated two IFNGS based on the above measurements into a characterizing type 1 IFN related gene signature as well as an activity-dependent type 2 IFN related gene signature.

3.9.9.3.2.1 Type 1 IFN relation				13 genes (6 unique)
Abbreviation	Gene	Included in	Function  (according to Genecards.org)	
ISG15	ISG15 ubiquitin-like modifier	M1.2	Protein Coding gene. Diseases associated with ISG15 include Immunodeficiency 38 With Basal Ganglia Calcification and Influenza. Among its related pathways are RIG-I/MDA5 mediated induction of IFN-alpha/beta pathways and Innate Immune System. Gene Ontology (GO) annotations related to this gene include protein tag. An important paralog of this gene is UBC.	

IFI44	interferon-induced protein 44	M1.2	Protein Coding gene. Diseases associated with IFI44 include Hepatitis D and Potocki-Shaffer Syndrome. An important paralog of this gene is IFI44L.
IFI27	Interferon Alpha Inducible Protein 27	-	Protein Coding gene. Diseases associated with IFI27 include Hepatitis C and Oral Leukoplakia. Among its related pathways are Innate Immune System and Interferon gamma signaling. Gene Ontology (GO) annotations related to this gene include RNA polymerase II activating transcription factor binding and lamin binding. An important paralog of this gene is IFI27L2.
CXCL10	chemokine (C-X-C motif) ligand 10	M1.2	Protein Coding gene. Diseases associated with CXCL10 include Periapical Periodontitis and Viral Encephalitis. Among its related pathways are Innate Immune System and PEDF Induced Signaling. Gene Ontology (GO) annotations related to this gene include signaling receptor binding and chemokine activity. An important paralog of this gene is CXCL9.
RSAD2	radical S-adenosyl methionine domain containing 2	M1.2	Protein Coding gene. Diseases associated with RSAD2 include Yellow Fever and Chikungunya. Among its related pathways are Innate Immune System and Interferon gamma signaling. Gene Ontology (GO) annotations related to this gene include protein self-association and iron-sulfur cluster binding.

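### Does SAP 5.2.3 leave the interferon score too loosely defined for confirmatory tests 1b and 2b?

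*SAP*

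**What the plan says.** SAP 3.1 and 6.2 split alpha between VO2max and fatigue, and test effect modification (1b, 2b) only after a significant treatment effect (1a, 2a). SAP 6.1 enters IFNGS as a continuous variable with its interactions. SAP 5.2.3 describes the measurement as a baseline sample, "Analyzed by Nanostring for genes related to IFN-signaling" (with a citation to the three-module paper), housekeeping normalisation, and finally "Calculating a standardized z-score compared to the expression from 9 healthy controls".

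The protocol holds the computational detail. Section 3.9.9 states that "we will determine both a Z-score and a Geomean mRNA expression score for all subjects". Section 3.9.9.1 gives the gene-level formula, whose numerator is "Gene Count - Mean (HC gene expression)" and whose denominator is the SD in healthy controls. It adds: "This Z-Score can then be averaged for each module to give a standardized mRNA expression score". Section 3.9.9.2 introduces the other score: "Alternatively, the geometric mean of mRNA expressed genes can be calculated as". Section 3.9.9.3.1 lists "modules defined by them as related to IFNGS for SLE; M1.2, M3.4 and M5.12". Section 3.9.9.3.2 adds a two-score method with "a characterizing type 1 IFN related gene signature as well as an activity-dependent type 2 IFN related gene signature".

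**The concern.** The interferon hypothesis is tested confirmatorily only in 1b and 2b, and both depend on one number per patient. Taken alone, SAP 5.2.3 does not let a reader compute that number. The protocol lists several gene sets, two kinds of score and a formula without a log step, and the SAP does not say which of these it adopts. If the score were chosen after the results were seen, the Bonferroni split and the hierarchy would no longer hold the error rate at its stated level. If expression counts are strongly right-skewed, a few patients could also dominate a linear interaction on the count scale. The only model sensitivity analysis in SAP 6.1 is sex by time, and the displays by IFN percentile are descriptive.

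**Working it through.** **Gene pool.** Protocol Table 2 lists 20 + 17 + 8 = 45 module genes. The two-score method adds 6 + 7 unique genes: 45 + 6 + 7 = 58, the total stated in protocol 3.9.9.3. The 13-gene type 1 score shares 6 genes with M1.2 and 1 with M3.4, and has 6 of its own.

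**What the documents settle.**
- Timing: baseline (SAP 5.2.3; SAP 12.1, Table 3).
- Form: continuous (SAP 6.1).
- Type of score: z-score (SAP 5.2.3), so the geometric mean is not the SAP's choice.
- Scale: the only z-score formula (protocol 3.9.9.1) is on counts. No log-transformed z-score appears in either document.
- Averaging: within module (protocol 3.9.9.1).
- Gene set: narrowed to the three-module source by the SAP citation. SAP 5.3.11 makes IFN-beta and IFN-gamma expression separate exploratory outcomes. Protocol 2.1 relates M1.2 to IFN-alpha, M3.4 to alpha and beta with some gamma, and M5.12 to all three. M1.2 is therefore the natural reading of the SAP's type 1 signature, though this is an inference.

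**What stays open.** Whether modules are combined, and how. Pooling all genes would weight the modules 20/45 = 0.44, 17/45 = 0.38 and 8/45 = 0.18; a mean of module means would weight each 0.33.

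**Type I error.** Alpha per endpoint is 0.05/2 = 0.025. The simulation regressed change on arm, score and their product by ordinary least squares, under no modification, with 20,000 runs per setting. Change SDs were 2.15 and 3.34 (protocol 3.9.18). Assumptions not in the documents: patient log2 SD 0.5 to 2, within-module gene correlation 0.5 or 0.8, between-module factor correlation 0.7 or 0.9, and control log2 SD 0.5 with 9 controls.

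| Scores from which the best p-value is kept | n=55 | n=40 |
|---|---|---|
| One fixed score | 0.023–0.027 | 0.024–0.030 |
| Count or log, one module | 0.029–0.041 | 0.029–0.046 |
| Three modules, one scale | 0.046–0.069 | 0.050–0.071 |
| All six | 0.056–0.100 | 0.060–0.102 |

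The values for independent scores, 1 − 0.975^k, are 0.049, 0.073 and 0.141 for k = 2, 3 and 6. At n=55 the simulated values lie below these because the scores are correlated. A second simulation used one latent interferon activity and six other candidates (M1.2, all 45 genes and the 13-gene score, each on counts and logs). It gave 0.038–0.049 for the best of six. All these figures are two-sided. Hypothesis 1b is directional, and false positives in the hypothesised direction are about half as many (0.031–0.054 for all six, against 0.0125), so the relative inflation is unchanged.

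**Scale.** With an assumed control log2 SD of 0.5, a gene expressed 8-fold has z = 3/0.5 = 6.0 on logs. On counts the control mean is 1.062 and the SD 0.379, so z = (8 − 1.062)/0.379 = 18.3. The top patient's mean share of the score's sum of squares is then 16–46% on counts and 12% on logs, as patient log2 SD runs from 0.5 to 2.

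Power for 1b at an assumed slope of 1.9 ml/kg/min per SD (n=55):
- If modification is linear in log expression, the log score has 53–55%. The count score falls from 51–52% at log2 SD 0.5 to 31–35% at log2 SD 2.
- If modification is linear in counts, the log score loses 0–9 points.

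At slope 2.6 the log score gains 2–32 points or loses 1–13. Neither slope comes from the documents. The model also adds modification on top of a residual SD of 3.34, which makes the exercise-arm SD √(3.34² + 1.9²) = 3.84 or √(3.34² + 2.6²) = 4.23. Holding the total at 3.34 raises power at slope 1.9 to about 66%.

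**The case for a change.** The strongest case is that two analysts following the SAP could compute different moderators, and that afterwards nobody could show the choice was made without sight of the results. The protocol itself points in different directions: 3.9.18 identifies high IFNGS with M3.4 and M5.12, 3.9.9.3.4 expects a reduced effect with a positive score in any module, and the SAP speaks of type 1 activity. With a true modification of 2.0 ml/kg/min per SD, the six candidates of the second simulation disagreed on significance in 21–28% of trials. Naming the genes would cost a line.

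Part of this stands: no sentence names the module or combination used for 1b and 2b. The rest is weaker. The protocol's high-IFNGS group belongs to a sample-size argument that SAP 4 recasts as a median split of one IFN score and that SAP 6.1 replaces with a continuous term. Half of the disagreeing candidates use a log scale that the documents never offer. Correlated tests with power of 0.44–0.60 will often fall on opposite sides of a threshold, so disagreement alone does not make any one of them invalid.

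The best argument for logs is that the possible power gain exceeds the possible loss in the settings tried. That depends on assumed skewness and on assumed linearity in log expression. At log2 SD 0.5 the scale hardly matters for power. Fragility does not favour either scale: dropping the top exercise-arm patient removes significance in 13–19% (count) versus 13–15% (log) of significant results under a log-linear truth, and in 19–51% versus 19–52% under a count-linear truth.

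**Conclusion.** No change to the plan follows. The scale, the within-module average, the timing and the continuous form can all be read from the SAP and protocol together. The SAP's citation and its separate IFN-beta and IFN-gamma outcomes narrow the gene set, with M1.2 as the natural reading. The remaining choice of module or combination is a detail that the analyst settles when computing the score. SAP 6.3 says the code will be made available, so the choice will be visible.

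Any one score fixed beforehand gives a test of close to nominal size (0.023–0.027 at n=55). The larger figures, 0.046–0.069 over three modules and 0.056–0.100 over all six scores, describe deliberate selection of the best p-value, which the SAP does not plan. They are upper bounds: they rest on assumed expression spread and correlations, use least squares in place of the constrained mixed model, and ignore the gate on 1a and 2a. Moving to log2 would be a fair alternative with its own possible loss of up to 13 points, so it does not correct an error. The judgement covers only the supplied text; the published protocol and the signature paper cited by the SAP may say more.
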